3.2 SUMMARY OF DATA SOURCES

[Table 1](#) summarises the main characteristics of the automated primary health databases that are proposed for study implementation. A focused feasibility evaluation has confirmed the availability of key information, lag time for data downloads, and other key parameters. Custodians of the three databases have confirmed their interest in participating in the study.

A search of the literature has identified studies on atrial fibrillation in each of the three databases. In the CPRD, a study on the incidence of atrial fibrillation based on recorded GP diagnoses confirmed the identified cases through questionnaires sent to GPs [[R10-0421](#)]. In the Danish national databases, the validity of the diagnoses of atrial fibrillation (AF) and atrial flutter (AFL) recorded in the Danish National Patient Registry has recently been reported to be high [[R13-5417](#)]. According to this review of medical records for incident cases of AF and/or AFL in the Diet, Cancer, and Health cohort study, the positive predictive value of the combined diagnosis of AF and/or AFL was 92.6% (95% confidence interval, 88.8%-95.2%), with no difference between sexes. A specified diagnosis of AFL was rarely used and was not reliable to distinguish between cases of AF and AFL. Using data from Aarhus, the risk of AF/AFL associated with the use of non-steroidal anti-inflammatory drugs (NSAIDs) has been reported [[P11-08175](#)]. Finally, an unpublished reference was found for a study on patients with atrial fibrillation performed using Cegedim, France; no details are available [[R11-4018](#)].

Table 1 Characteristics of automated primary health care databases available in the UK, Denmark, and France

Description	UK (N = 61,634.6) ¹ CPRD	Denmark (N = 5,552.0) Patient and Prescription National Databases	France (N = 64,350.8) ¹ Cegecim Strategic Data

Database type
 
Database population²
 
Approximate proportion of the country's population covered by the database
 
Potential number of dabigatran etexilate users in 2012 captured in the database (based on BI sales estimates)
	
Primary health care electronic medical record database plus linkage to HES and other data
 
5.1 million
 
8%
 
8,000
	
National health record databases capable of linkage with other databases though the unique personal number assigned by the Central Person Registry
 
5.6 million
 
100%
 
15,000
	
Primary health care electronic medical record database
 
2.6 million
 
4%
 
4,000

Data on medications
 
Dose
 
Duration
	
GP prescriptions
 
Prescribed dose
 
As indicated by the written prescription
	
Pharmacy-dispensed prescriptions, reimbursed and unreimbursed.
 
Formulation strength
 
Based on dispensed prescriptions
	
GP prescriptions and Cardiologists prescription
 
Prescribed dose
 
As indicated by the written prescription

Table 1 (cont'd) Characteristics of automated primary health care databases available in the UK, Denmark, and France

Clinical indication	Associated with new courses of medications, but completeness is variable. Computerised free-text information is available for review.	Not specifically recorded but based on proxies	Associated with new courses of medications, but completeness is variable
Outpatient diagnosis	Yes (Read codes)	Only outpatient hospital diagnosis in the patient register (ICD-10-CM); primary care diagnoses in DAMD (ICPC codes)	Yes (ICD-10-CM)
Hospital diagnosis	Recorded by GPs and partial linkage to HES (Read and ICD-10-CM)	Yes (ICD-10-CM)	No
Access to medical records	GPs, and partial linkage to HES	Partial access to hospitals, only in some regions	No
Prior atrial fibrillation assessment	Yes, based on recorded Read codes and validated through GP survey [R10-0421]	Yes (AF diagnosis with positive predictive value of 93%) [R13-5417]	Yes, based on recorded information, but unpublished [R11-4018]
Lifestyle risk factors	Yes	Yes, in DAMD	Yes
Data availability	Since 1987	Since 1994	Since 1994
Updates	At 3- to 4-month intervals	Yearly	Monthly
Approximate time lag	6-12 weeks	2012 data available in 3-4Q 2013	2-7 months

GP = general practitioner; CPRD = Clinical Practice Research Datalink; HES = Hospital Episode Statistics (database); ICPC = International Classification of Primary Care; UK = United Kingdom.

1 In thousands. Population data from EuroStat. 2009. Accessed 2 Aug 2011. Available at: Website: epp.eurostat.ec.europa.eu/portal/page/portal/product_details/publication?p_product_code=KS-QA-09-047.

2 Based on “active” patients (i.e., patients having consulted a GP at least once in the year).

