- The Danish General Practice Database (DAMD) provides information from selected general practices at the national level, with the purposes of promoting and improving the quality of care in general practice and providing data for research concerning general practice. The website for the DAMD (website: dak-e.dk/flx/en/danish-general-practice-database/) reports that “Key data are transferred from the GP’s electronic health record system to the database. Most data are automatically collected by the Sentinel Data Capture—these data include prescribed drugs, National Health Service disbursement codes, laboratory analysis results, and International Classification of Primary Care (ICPC) diagnoses. Additional information is collected via pop-up screens which the GP has to fill in during the consultation. The pop-up screen is designed specific for the chronic disease in question or for a particular research project. All data are linked to the patient’s personal ID and the time stamp for the consultation and stored in the DAMD.” Hosted at the University of Southern Denmark, the database covered approximately 1 million population in 2012, but this is increasing through time [[R13-5415](#)]. Access to almost the entire covered population is also possible for selected information.

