3.3.5 Treatment indication

The indication or reason for treatment will be assessed according to the data available in the selected databases. The indication for a new course of treatment is most often not recorded in a systematic way in existing databases, and the degree of completeness of recording this information is variable across databases. In some primary health databases like the CPRD, the indication for a prescription is usually recorded the first time a new drug is prescribed by the general practitioner (GP). Similarly, the French Cegedim systematically records a clinical diagnosis associated with specific courses of medications. However, in the Danish national databases, data on indication is based on proxies.

It is expected that a proportion of new courses of dabigatran etexilate may not have a clearly associated clinical indication. Therefore, proxies for indication will be created using computer algorithms based on sets of diagnostic, procedural, and medication codes. These algorithms will be included in the detailed, database-specific study protocol. These indication-proxy algorithms will be helpful to search a time period before or concurrent with the index date. A minimum period of 1 year prior to the index date is considered the baseline period for determination of the clinical indication. However, all available historical data on diseases and medications might be used to develop valid algorithms for some indications.

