3.5.2 Off-label use definition

The definition of off-label use of oral dabigatran etexilate outside AF will be based on the use for a disease or medical condition other than the labelled indications and patient sub-groups given in Section [3.5.1](#). The dabigatran indications approved at the time of the index date will be used to define off-label use for each new user identified in the study period. In the absence of labelled indications, potential off-label use could include, but is not limited to, the following:

- General thrombosis prophylaxis other than hip and knee orthopaedic surgery.
- Treatment of deep vein thrombosis (DVT) and pulmonary embolism (PE) and prevention of recurrent DVT and PE in adults (CHMP opinion 25 April 2014), until Commission Decision
- Anticoagulation for patients with heart valve replacement or a stent.
- General prophylaxis or treatment of a thrombus in any site.
- Patients with hypercoagulability (e.g., factor V Leiden thrombophilia).

A preliminary list of ICD-10-CM codes to identify these conditions is provided in [Table 5](#). The final list will be included in the detailed, database-specific study protocol. In addition, the set of algorithms to be used as proxies for identification of potential clinical indications will be defined and described in the detailed, database-specific study protocol. These proxies will be based on codes for the presence of certain diseases and clinical conditions and the use of certain medications (e.g., use of other oral anticoagulants).

Because dabigatran etexilate has been approved for use only in adults, any identified use in the pediatric groups of age will be considered off-label. New users of dabigatran etexilate aged younger than 18 years at the index date will be considered in the pediatric population.

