3.7.1 Main analysis by indication

The main analysis will be to estimate (with 95% confidence intervals) the prevalence proportion of off-label use among new users of dabigatran etexilate during the overall study period in each of the study populations. This will include potential off-label clinical indications and contraindications. The proportion of each of the most common off-label use indications will be described among the overall off-label use group. The proportion of identified users in the pediatric age subgroup will be described.

In addition, separately for each approved clinical indication, the risk profile and use of selected drugs among new users of dabigatran etexilate will be described.

The distribution of the dispensed formulation strength or the daily prescribed dose at the index date based on the index prescription will be described, overall and by on-label and off-label indication sub-group. The proportion of new users within the primary VTE prevention subgroup with one or more follow-up prescriptions after the recommended treatment duration will be described. The follow-up prescriptions will be assessed in the 90-day time window after the index prescription.

To evaluate the differences between sub-groups by indication, proportions for categorical variables and means for continuous variables will be estimated (with 95% confidence intervals) within each sub-group. If appropriate, medians will be used instead of means when the variables of interest do not assume a normal distribution.

All the results will be presented for each country-specific database. In addition, for France, all the data will be stratified by type of physician panel: primary care or cardiologist. As part of the analysis, tables presenting the results will be generated. Table shells for the key descriptive analyses will be developed for the detailed, database-specific protocol.

A weighted, pooled prevalence of off-label use among new users of dabigatran etexilate for the entire study population (CPRD, Cegedim, and Danish national databases) will be estimated (with 95% confidence intervals) when the individual results of all three databases are available.

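### Danish GP diagnoses cover only about 18% of the population, so the single national off-label proportion can count some on-label users as off-label, and nothing planned measures how many

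*Protocol*

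**What the plan says.** - **Population.** Table 1 (section 3.2) enters Denmark as the whole country: 5.6 million people, 100% coverage and 15,000 potential dabigatran users in 2012.
- **Diagnoses.** Hospital diagnoses come from the national patient register. For outpatient diagnoses Table 1 gives "Only outpatient hospital diagnosis in the patient register (ICD-10-CM); primary care diagnoses in DAMD (ICPC codes"). Section 3.1.3 says of DAMD that "the database covered approximately 1 million population in 2012, but this is increasing through time", and adds: "Access to almost the entire covered population is also possible for selected information". It does not say which information that is.
- **Indication.** Section 3.3.5: "However, in the Danish national databases, data on indication is based on proxies". Section 3.5.2: "These proxies will be based on codes for the presence of certain diseases and clinical conditions and the use of certain medications". The algorithms are left to the database-specific protocol.
- **Off-label codes.** In Table 5 the malignancy and antiphospholipid rows apply when no Table 3 or Table 4 code is present. The stent and bypass row applies when AF is absent.
- **Two levels.** Section 3.5.1 has a broad on-label level based on the main indication code, and a restrictive level that removes, among others, low-risk non-valvular AF.
- **Analysis.** Section 3.7.1: "The main analysis will be to estimate (with 95% confidence intervals) the prevalence proportion of off-label use among new users of dabigatran etexilate" in each study population, followed by a weighted pooled estimate. The only split within a country is the French one: "In addition, for France, all the data will be stratified by type of physician panel: primary care or cardiologist".
- **Validity.** Section 3.2 reports that "the positive predictive value of the combined diagnosis of AF and/or AFL was 92.6" per cent in the Danish register. Manual profile review is planned in the UK database only (section 3.3.5.1).

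**The concern.** A diagnosis that only a GP has recorded can be seen for Danish users inside DAMD and not for those outside it. For most Danish users the proxy algorithm therefore works from hospital codes and dispensed medicines alone. Where the rule depends on an on-label code being absent, a missing code and a true absence look the same.

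The Danish proportion would then mix real off-label use with under-recording. A difference between Denmark and the UK or France could reflect the data source rather than prescribing, and the pooled figure would inherit it. The confidence interval would not show the problem, because it reflects sampling error only.

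**Working it through.** **1. The plan's own precision.** Exact binomial limits reproduce all 20 intervals in Table 2 to one decimal. For 5% off-label at n = 5,000 they are 4.4% to 5.6%, a half-width of (5.6 − 4.4)/2 = 0.6 points.

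**2. Coverage.** 1.0/5.6 = 17.9% of the population is in DAMD and 82.1% is outside. With users spread evenly, 0.821 × 15,000 ≈ 12,300 of the potential 2012 users have no GP diagnoses.

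**3. Where the stated rules produce the error, outside DAMD.**
- *Either level:* AF is recorded only by the GP and an off-label code is in the hospital data. Examples are a coronary stent, or malignancy with no other Table 3 or Table 4 code. The AF code that would block the Table 5 row is not seen.
- *Restrictive level only:* AF is in the hospital data, but the qualifying diabetes or hypertension is recorded only by the GP. The patient looks low-risk unless age 75 or over, another listed risk factor or a medication proxy qualifies them. Under the August 2011 label this concerns ages 65 to 74. Under the December 2013 wording, diabetes or hypertension counts without that age condition.

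**4. What the cited validation measures.** A positive predictive value of 92.6% says that a recorded AF code is usually right. The error here is an on-label diagnosis with no code, which is a matter of sensitivity, and no sensitivity is given. The UK profiles include GP diagnoses and, where available, free text, so reviewing them does not test an algorithm that lacks GP codes.

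**5. Possible size.** Let c = 0.179 (DAMD coverage), t = true off-label proportion, and g = share of on-label users outside DAMD who are missed. The value of g is not in the protocol; it is assumed here. Counting every missed user as off-label (worst case):

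apparent = c·t + (1 − c)·[t + (1 − t)·g] = t + (1 − c)(1 − t)·g

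With t = 5%, the added part is 0.821 × 0.95 × g:

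| g (assumed) | added, points | apparent |
|---|---|---|
| 1% | 0.8 | 5.8% |
| 2% | 1.6 | 6.6% |
| 5% | 3.9 | 8.9% |
| 10% | 7.8 | 12.8% |

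**6. Carry-over to the pooled estimate.** The weights are not stated. A Danish bias of 3.9 points adds 3.9/3 = 1.3 points with equal weights. With weights of 15,000 : 8,000 : 4,000 (the potential users in Table 1) it adds 3.9 × 15/27 = 2.2 points.

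**7. Size of the linked subset.** If accrual stops at 5,000 Danish users, 0.179 × 5,000 ≈ 893 are in DAMD, with an exact 95% interval at 5% of 3.7% to 6.7%. With all 15,000 potential users it would be about 2,679 (4.2% to 5.9%).

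**The case against.** A reader might infer that every Danish user without an on-label code is counted as off-label. The available text does not say so. Section 3.5.2 defines off-label use by another condition, Table 5 works from positive off-label codes, and section 3.3.5 expects some courses to have no clear indication. The Appendix 4 diagram of categories is not in the text at hand. A patient with GP-only AF and no other code may be handled differently, and the claim has to stay with the two situations in step 3 of the working.

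Several other points limit the concern:
- GP-treated diabetes or hypertension can leave a dispensing record. The prescription database starts in 1994, and hospital outpatient visits are recorded from 1995. Some patients will be recovered this way.
- Missing risk factors do not affect the broad level.
- The coverage figure is from 2012 and rising, with the unclear remark about wider access.
- Section 4 acknowledges misclassification and missing indication data in general terms, and the ENCePP checklist says missing information will be described.

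A reader might also conclude that DAMD-linked users should become the main Danish population. The protocol's numbers do not support that. At the planned 5,000 users the subset is about 893, below the 2,000 to 5,000 that section 3.3.6 calls acceptable. It also comes from selected practices, and national coverage would be given up.

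Leaving the algorithms to a later document is not a full answer. The population, the single proportion and the stratification are set in the common protocol, and no algorithm can read a diagnosis that is not in the data.

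**Conclusion.** The concern holds in limited form. The plan estimates and pools one national Danish proportion from two groups with unequal diagnostic information. Its stated rules can turn some on-label users outside DAMD into apparent off-label users, and nothing planned measures how many.

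The size is unknown. The figures of 5.8%, 8.9% and 12.8% for a true 5% are upper values for assumed missed shares of 1%, 5% and 10%. They rest on 2012 DAMD coverage, an even spread of users, and every missed user being counted as off-label. They do show that a missed share of about 1% could already add more (0.8 points) than the half-width the study was sized on (0.6 points). The documents do not establish that the bias is large.

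**What to change.** In section 3.7.1, for the Danish component:

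1. Keep all national new users as the main Danish population, and report the off-label proportion separately for DAMD-covered and non-covered users, at both levels.
2. Within DAMD-linked users, run the algorithm with and without GP codes. Report how many change from off-label to on-label when GP codes are added, and any that move the other way.
3. Use that share to give a corrected or bounded national and pooled estimate as a sensitivity analysis.
4. Show users with no identified indication as a category of their own.

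The cost is extra analysis: one more run of the same algorithm and a few table columns. Approval from the DAMD board is already to be requested (section 7), and DAMD data carry the personal identifier (section 3.1.3).

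The linked subset is less precise. With 893 users, a true off-label share of 5% and a missed share of 1%, only about 8 would change class (893 × 0.95 × 0.01 = 8.5), so the correction needs its own interval. It also assumes that DAMD practices resemble the others, which should be stated with the result.

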3.3 STUDY POPULATION

The study population will include new users of dabigatran etexilate in the study period. *New user* will be defined as those patients who initiate treatment with dabigatran etexilate during the study period and who have not used it during the previous 1 year.

The *study period* will encompass the time period from the launch of dabigatran etexilate for the new indication in each country until the target number of new users is reached in each selected country-specific database. The study period and its length could therefore be different for each country-specific study.

3.3.1 Monitoring of dabigatran etexilate users

The first step in this study will be to monitor periodically the number of dabigatran etexilate users until the target number of new users has been reached to implement the study. The number of patients receiving prescriptions for dabigatran etexilate (irrespective of indication or dosage) will be monitored in the selected databases. The timing of the start and periodicity of the monitoring will be determined based on the lag time and update schedule for prescription data in each specific database. See [Table 1](#).

3.3.2 Index prescription

The first captured prescription for dabigatran etexilate in the study period for each new user in the source population will be the *index prescription*. The ATC code for dabigatran etexilate is B01AE07 (see [Appendix 3](#)).

3.3.3 Index date

The *index date* will be defined as the date on which each identified new user receives the first prescription for dabigatran etexilate.

3.3.4 Inclusion criteria

Patients who received a new prescription of dabigatran etexilate will be required to meet the following criteria, as ascertained from each of the final selected automated databases:

- Have at least 1 year of enrolment in the electronic database.
- Have not been prescribed dabigatran etexilate during the 1-year period prior to the index date. A minimum of 1-year period prior to the index date is considered the “baseline period.”

No age restrictions or exclusion criteria will be applied. This will allow for the characterisation of all users of dabigatran etexilate according to each potential indication for which the medication is being used, including on-label indications and potential off-label uses. This will include any pediatric population and patients with contraindications (e.g., severe renal impairment).

Specific inclusion criteria for each database might need to be applied. These criteria will be specified in the adapted protocol for each database before study implementation. As an example, in CPRD only patients with permanent registration status in “up to standard” participant general practices will be included in the study.

3.3.5 Treatment indication

The indication or reason for treatment will be assessed according to the data available in the selected databases. The indication for a new course of treatment is most often not recorded in a systematic way in existing databases, and the degree of completeness of recording this information is variable across databases. In some primary health databases like the CPRD, the indication for a prescription is usually recorded the first time a new drug is prescribed by the general practitioner (GP). Similarly, the French Cegedim systematically records a clinical diagnosis associated with specific courses of medications. However, in the Danish national databases, data on indication is based on proxies.

It is expected that a proportion of new courses of dabigatran etexilate may not have a clearly associated clinical indication. Therefore, proxies for indication will be created using computer algorithms based on sets of diagnostic, procedural, and medication codes. These algorithms will be included in the detailed, database-specific study protocol. These indication-proxy algorithms will be helpful to search a time period before or concurrent with the index date. A minimum period of 1 year prior to the index date is considered the baseline period for determination of the clinical indication. However, all available historical data on diseases and medications might be used to develop valid algorithms for some indications.

